5.1.3 Study Plan

An overview of assessments and study vaccinations is provided in the [Table of Study Procedures](#).

Each potential subject will sign and date the ICF. In addition to the Screening Visit, included subjects will attend 8 study visits, will receive 4 follow-up phone calls, and will be contacted 6 months after the last Visit for a safety follow-up.

Vaccination

All subjects will receive 3 injections of either CYD dengue vaccine or placebo at Day (D) 0, Month (M) 6, and M12.

Blood sampling

A number of immunological, hematological and biochemical parameters (see [Section 5.2.3](#)) will be assessed at screening (unless the tests have already been performed as part of routine follow-up within the 4-week time window). The subject's dengue serostatus will be determined by a RDT or an ELISA during the Screening Visit.

Dengue, YF, and Zika baseline status will be assessed at D0.

Dengue vaccinal viremia will be assessed at D7 and D14 post-Inj 1.

Dengue neutralizing antibody (Ab) levels will be assessed at baseline (V01; prior to Inj 1) and 28 days after each injection.

If no HIV viral load and CD4 count results are available prior to each injection (ie, tests have not been performed within 2 months before injection visit), tests will be performed to ensure that results are available at the time of injection visit.

HIV viral load and CD4 count will be assessed 28 days after each injection. In case an increase in HIV viral load (plasma HIV-1 RNA > 1000 copies/mL 28 days post-injection after having been undetectable [< 50 copies/mL] pre-injection) or a decrease in CD4 count (decrease greater than 30% 28 days post-injection compared to the pre-injection value) is observed, a second blood sample is to be taken 4 weeks later for confirmation, as it is current local practice to confirm abnormal and significant deterioration of HIV condition related results (48) (see [Section 5.5](#)).

A summary of blood samplings is provided in [Table 5.1](#).

Table 5.1: Blood Sampling Volume (mL) per Visit for all Assessments

Visit (V) Number	Scr.	V01	V02	V03	V04	V05	V06	V07	V08
Trial timelines (Days/Months)	-D28 to -D0	Inj 1 (D0)	Inj 1 +7D	Inj 1 +14D	Inj 1 +28D	Inj 2 (M6)	Inj 2 +28D	Inj 3 (M12)	Inj 3 +28D
Time Windows (Days)			+3	+3	+14	±20	+14	±20	+14
Approximate volume for each assessment (mL)									
Serology (HBsAg, HCV Ab)*	5								
Hematology (hemoglobin, hematocrit, platelet count, white blood cells count)*	3								
Biochemistry (AST, ALT, urea, creatinine)*	5								
Previous exposure to dengue using RDT or dengue ELISA	1†								
Dengue, YF, and Zika serostatus		5							
Dengue neutralizing Abs		2			2		2		2
Serum sample for retesting		2			2		2		2
Dengue vaccinal viremia			4	4					
CD4 count	‡				10	‡	10	‡	10
HIV-1 viral load	‡				10	‡	10	‡	10
Total volume for each subject	14§	9	4	4	24		24		24

* HBsAg and HCV tests will not be performed in case information is already available in subject's medical history. If serology, hematology, and biochemistry results are available and were obtain within 4 weeks before first injection, tests do not need to be performed again.

† Tests will be performed sequentially. RDT will be performed first, and IgG ELISA will only be performed on subjects who tested negative for RDT. Tests will be done by the Investigator, following the RDT or ELISA Manufacturer's instructions. Subjects who previously tested negative by RDT can be re-screened using dengue IgG ELISA.

‡ Pre-injection CD4 count and HIV viral load will come from routine periodical tests of subjects as per local guidelines. For subjects for whom CD4 count and HIV viral load have not been assessed within 2 months before the Screening Visit, the Investigator will perform tests to ensure that results are available at the time of Visit 1. Likewise, if CD4 count and HIV viral load have not been tested within 2 months before Inj 2 or Inj 3 (for checking contraindication), the Investigator will perform tests to ensure that results are available before the corresponding vaccination visit.

§ This volume is indicative only as it may differ between local laboratories. It does not include the volume that might possibly be required for the assessment of baseline CD4 count (10 mL) or HIV viral count (10 mL) in some subject (ie, subjects for whom CD4 count and HIV viral count have not been assessed within 2 months before the Screening Visit).

Collection of safety data

Safety data will be collected following each injection. Clinical site personnel will record immediate AEs that occur within the 30 minutes after injection. Subjects will record in the diary card (DC) information about solicited injection site reactions from D0 to D7 post-injection, about solicited systemic reactions from D0 to D14 post-injection, and unsolicited AEs occurring up to 28 days post-injection. Information on SAEs will be reported throughout the study (See [Section 10.1](#) and Operating Guidelines for more information). Serious and non-serious AEs of special interest (AESIs) will be collected in defined time windows according to the type of AESI.

DCs will be provided to subjects to collect information on SAEs in-between injections (ie, from 28 days to 6 months post-Inj 1; and from 28 days to 6 months post-Inj 2) A memory aid (MA) will be provided to subjects to help them record SAEs during the 6 months safety follow-up (from 28 days post-Inj 3 to 6 months after last injection). Subjects are to contact the Investigator (within the first 5 days after fever onset) in case of hospitalization for suspected dengue disease at any time during the study for virological confirmation of the disease.

Clinical site personnel will review the safety data with the subjects during post-injection visits.

5.1.4 Visit Procedures

All information collected during the study visits must be reported into the source documents. For eligible subjects, the information collected will also be recorded in the electronic case report form (CRF) at V01.

Screening Visit (Scr.; D-28 to D0): Inclusion, Physical/Clinical Examination and Blood Sample of Potential Subjects

For all subjects (see [Section 5.2.3](#))

- 1) Present the study to the subject in more details, answer any of her/his questions, and ensure that she/he has been informed of all aspects of the study that are relevant to their decision to participate.
- 2) Obtain the ICF signed and dated by the subject, and date and sign the ICF (only the Investigator or sub-Investigator). The Investigator will keep the original document and give the other one to the subject.
- 3) Review the inclusion and exclusion criteria for eligibility.
- 4) Check and collect the subject's significant medical history (including ART-related information).
- 5) Check and collect the subject's history of dengue infection/vaccination, YF vaccination/infection, and Zika infection.
- 6) Perform a physical examination.
- 7) Obtain the blood sample for screening tests (including assessment of previous exposure to dengue using the RDT or dengue IgG ELISA; see [Section 7.1](#) for detailed instructions regarding the handling of blood samples), record the date of collection.

It is important to note that, if the attempt(s) to collect blood is (are) unsuccessful, the subject should be given the opportunity for another attempt, even on another day within the Visit window. If ultimately a blood sample cannot be obtained, the reason will be recorded in the source document. In that case, the subject will not participate in the study.

- 8) Call the Interactive Response Technology (IRT) in order to get the subject's inclusion number
- 9) Remind the subject to call the study center if a serious medical event occurs
- 10) Arrange an appointment for Visit 1 (V01)

The Visit may be postponed once if the subject is temporarily not eligible at the Screening Visit.

Notes:

- Subjects who previously tested negative by RDT for previous exposure to dengue can be re-screened using IgG ELISA. Subjects who are re-screened will be allocated a new subject number.
- If a subject is eligible but not randomized during the ESDR hold, the subject will be asked to come back to the site after the hold. The subject will then be re-screened and randomized. However, the subject will not be re-tested for previous exposure to dengue by RDT or IgG ELISA. It is to be noted that subjects that are re-screened will be allocated a new subject number.

Visit 1 (Inj 1 /D0): Randomization, Blood Sample, and Vaccination of Eligible Subjects

Once dengue previous exposure has been identified using RDT or dengue IgG ELISA, the Visit 1 procedures may be undertaken.

- 1) Review the inclusion and exclusion criteria and confirm the eligibility
- 2) Collect demographic (year of birth and gender) and body stature (height and weight) data
- 3) Check and collect the subject's significant medical history (including ART-related information)
- 4) Check and collect the subject's history of dengue vaccination/infection, of YF vaccination/infection, and of Zika infection
- 5) Perform a physical examination and record the subject's axillary temperature before injection
- 6) Check concomitant medications and record every reportable medication ongoing at the time of vaccination
- 7) Perform a urine pregnancy test for all women enrolled in the study
- 8) Obtain a blood sample (see [Section 7.1](#) for detailed instructions regarding the handling of blood samples), record the date of collection

It is important to note that, if the attempt(s) to collect blood is (are) unsuccessful, the subject should be given the opportunity for another attempt. If a blood sample cannot be obtained, the reason will be recorded in the blood sampling page of the CRF.

- 9) The person in charge of injections (“vaccinator”) or authorized designee contacts the IRT to obtain the assigned product to be administered
- 10) Inject the appropriate investigational product
- 11) Record the date of injection, the site, and side of injection and the route of administration, as well as the dose number of the vaccine
- 12) Affix the vaccine labels in the subject’s source documents
- 13) Keep the subject under observation for 30 minutes, and record any immediate AE reaction in the source document
- 14) Give the subject the first DC (DC1) to record any injection site reactions and systemic AEs, together with instructions for its completion, including explanations on the definition and use of intensity scales for collection of AEs
- 15) Give the subject a ruler to measure the size of any injection site reaction and a thermometer for temperature measurement, and instructions on how to use them
- 16) Remind the subject to call the study center if a serious medical event occurs
- 17) Arrange an appointment for the next visit (V02; at V01 + 7D [+ 3 day]).
- 18) Complete the relevant CRF pages for this Visit.

The visit may be postponed once if the subject is temporarily not eligible at Visit 1.

Note: The Screening Visit and Visit 1 can be simultaneous for subjects tested positive by RDT and whose tests have been performed in appropriate time windows (within 4 weeks before injection for hepatitis serology, hematology, and biochemistry; within 2 months for CD4 count and HIV viral load) as part of the subject’s routine follow-up.

Visit 2 (Inj 1+7D [+3 days]): Collection of Safety Information and Blood Sample

- 1) Check the information entered into DC1 by interviewing the subject and request information concerning any medical event, serious, or not, that may have occurred since Visit 1
- 2) Record any injection site reactions or systemic AEs and any reportable concomitant medications
- 3) Perform a physical examination and record the subject's axillary temperature (if necessary)
- 4) Obtain a blood sample (see [Section 7.1](#) for detailed instructions regarding the handling of blood samples), record the date of collection

It is important to note that, if the attempt(s) to collect blood is (are) unsuccessful, the subject should be given the opportunity for another attempt within the Visit window. If a blood sample cannot be obtained, the reason will be recorded in the blood sampling page of the CRF.

- 5) Remind the subject to call the study center if a serious medical event occurs.
- 6) Arrange an appointment for the next visit (V03; at V01 + 14D [+ 3 days]).
- 7) Complete the relevant CRF pages for this visit.

Visit 3 (Inj 1+14D [+3 days]): Collection of Safety Information and Blood Sample

- 1) Check the information entered into DC1 by interviewing the subject and request information concerning any medical event, serious, or not, that may have occurred since Visit 2
- 2) Record any AEs and any reportable concomitant medications
- 3) Perform a physical examination and record the subject's axillary temperature (if necessary)
- 4) Obtain a blood sample (see [Section 7.1](#) for detailed instructions regarding the handling of blood samples), record the date of collection

It is important to note that, if the attempt(s) to collect blood is (are) unsuccessful, the subject should be given the opportunity for another attempt within the Visit window. If a blood sample cannot be obtained, the reason will be recorded in the blood sampling page of the CRF.

- 5) Remind the subject to call the study center if a serious medical event occurs.
- 6) Arrange an appointment for the next visit (V04; at V01 + 28D [+14 days]).
- 7) Complete the relevant CRF pages for this visit.

Visit 4 (Inj 1+28D [+14 days]): Collection of Safety Information and Blood Sample

- 1) Collect DC1 and check the information entered into it by interviewing the subject and request information concerning any medical event, serious, or not, that may have occurred since Visit 3
- 2) Record any AEs and any reportable concomitant medications
- 3) Perform a physical examination and record the subject's axillary temperature (if necessary)
- 4) Obtain a blood sample (see [Section 7.1](#) for detailed instructions regarding the handling of blood samples), record the date of collection

It is important to note that, if the attempt(s) to collect blood is (are) unsuccessful, the subject should be given the opportunity for another attempt within the Visit window. If a blood sample cannot be obtained, the reason will be recorded in the blood sampling page of the CRF.

- 5) Remind the subject to call the study center if a serious medical event occurs
- 6) Provide the subject with DC2 and remind her/him to bring it back when she/he returns for Visit 5
- 7) Arrange an appointment for the next visit (V05; at V01 + 6 months (M6) [\pm 20 days])
- 8) Complete the relevant CRF pages for this visit

Visit 5 (Inj 2 [M6; \pm 20 days]): Collection of safety information and vaccination

- 1) Collect DC2 and check the information entered into it by interviewing the subject and request information concerning any medical event, serious, or not, that may have occurred since last Visit

- 2) Record any reportable concomitant medications
- 3) Perform a physical examination and record the subject's axillary temperature before injection
- 4) Check any contraindication to vaccination
- 5) Check for confirmation of previous exposure to dengue (from PRNT laboratory results)
- 6) Perform a urine pregnancy test for all women enrolled in the study
- 7) The person in charge of injections ("vaccinator") or authorized designee contacts the IRT to obtain the assigned product to be administered
- 8) Inject the appropriate investigational product
- 9) Record the date of injection, the site, and side of injection and the route of administration, as well as the dose number of the vaccine
- 10) Affix the vaccine labels in the subject's source documents
- 11) Keep the subject under observation for 30 minutes, and record any immediate AE in the source document
- 12) Give the subject the DC3 to record any injection site reactions and systemic AEs, together with instructions for its completion, including explanations on the definition and use of intensity scales for collection of AEs
- 13) Ensure subject still has the ruler to measure the size of any injection site reaction and the thermometer for temperature measurement
- 14) Remind the subject to call the study center if a serious medical event occurs
- 15) Arrange an appointment for the next visit (V06; at V05 + 28D [+ 14 days]). Remind the subject that she/he will be contacted twice by phone (PC1; at V05+ 7D [+3 days]; PC2; at V05 + 14D [+3 days]) by study staff.
- 16) Complete the relevant CRF pages for this visit.

Phone Call 1 (Inj 2+7D [+3 days]): Safety Follow-up Phone Call

Note: If PC1 falls on a weekend or a holiday, the telephone call may be made on the following business day.

- 1) Record relevant information concerning the subject's health status on the source document. If a SAE occurred follow the instructions in [Section 10](#) for reporting it.
- 2) Remind the subject to call the study center if a serious medical event occurs.
- 3) Remind the subject to record any AEs in the DC3.
- 4) Remind the subject of the appointment for the next visit (V06; at V05 + 28D [+14 days]).

Note: A follow-up visit can be arranged depending on the information provided during the phone call, at the Investigator's discretion.

Phone Call 2 (Inj 2+14D [+3 days]): Safety Follow-up Phone Call

Note: If PC2 falls on a weekend or a holiday, the telephone call may be made on the following business day.

- 1) Record relevant information concerning the subject's health status on the source document. If a SAE occurred follow the instructions in [Section 10](#) for reporting it.
- 2) Remind the subject to call the study center if a serious medical event occurs.
- 3) Remind the subject to record any AEs in the DC3, and to bring it back when she/he returns for Visit 6.
- 4) Remind the subject of the appointment for the next Visit (V06; at V05 + 28D [+14 days]).

Note: A follow-up visit can be arranged depending on the information provided during the phone call, at the Investigator's discretion.

Visit 6 (Inj 2+28D [+14 days]): Collection of Safety Information and Blood Sample

- 1) Collect DC3 and check the information entered into it by interviewing the subject and request information concerning any medical event, serious, or not, that may have occurred since Visit 5
- 2) Record any AEs and any reportable concomitant medications
- 3) Perform a physical examination and record the subject's axillary temperature (if necessary)
- 4) Remind the subject to call the study center if a serious medical event occurs
- 5) Obtain a blood sample (see [Section 7.1](#) for detailed instructions regarding the handling of blood samples), record the date of collection

It is important to note that, if the attempt(s) to collect blood is (are) unsuccessful, the subject should be given the opportunity for another attempt within the Visit window. If a blood sample cannot be obtained, the reason will be recorded in the blood sampling page of the CRF.

- 6) Provide the subject with DC4 and remind her/him to bring it back when she/he returns for Visit 7
- 7) Arrange an appointment for the next visit (V07; at V01 + 12 months (M12) [\pm 20 days])
- 8) Complete the relevant CRF pages for this visit

Visit 7 (Inj 3 [M12; \pm 20 days]): Collection of safety information and vaccination

Same procedure as for Visit 5. Subject is provided with DC5.

Phone Call 3 (Inj 3+7D [+3 days]): Safety Follow-up Phone Call

Same procedures as for Phone Call 1.

Phone Call 4 (Inj 3+14D [+3 days]): Safety Follow-up Phone Call

Same procedures as for Phone Call 2.

Visit 8 (Inj 3+28D [+14 days]): Collection of Safety Information and Blood Sample

- 1) Collect DC5 and check the information entered into it by interviewing the subject and request information concerning any medical event, serious, or not, that may have occurred since Visit 7
- 2) Record any AEs and any reportable concomitant medications
- 3) Perform a physical examination and record the subject's axillary temperature (if necessary)
- 4) Obtain a blood sample (see [Section 7.1](#) for detailed instructions regarding the handling of blood samples), record the date of collection

It is important to note that, if the attempt(s) to collect blood is (are) unsuccessful, the subject should be given the opportunity for another attempt within the Visit window. If a blood sample cannot be obtained, the reason will be recorded in the blood sampling page of the CRF.

- 5) Remind the subject to call the study center if a serious medical event occurs
- 6) Provide the subject with a MA
- 7) Remind the subject about the 6 months safety follow-up phone call (at M12 + 6 months [+30 days]).
- 8) Complete the relevant CRF pages for this visit and the End of Study CRF.

Safety Follow-up Telephone Call (6 months after last injection [+30 days]): Collection of SAEs

- 1) Ask the subject if she/he has experienced any SAE since the last injection. If an SAE occurred, follow the instructions in [Section 10](#) for reporting it.
- 2) Complete the relevant case report book (CRB) form.

Note: A follow-up visit can be arranged depending on the information provided during the phone call.

Follow-up of subjects with Related AEs or with AEs That Led to Study/Vaccination Discontinuation:

A subject who experiences an AE (whether serious or non-serious) during the study must be followed until the condition resolves, becomes stable, or becomes chronic (even after the end of the subject's participation in the study) if *either* of the following is true:

- The AE is considered by the Investigator to be related to the product administered
- The AE caused the discontinuation of the subject from the study or from vaccination

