† A follow-up visit can be arranged depending on the information provided during the phone call, at the Investigator's discretion. In the case of the 6-month follow-up phone call, this can be anticipated to perform the 6 months follow up after the last vaccination in case of early termination.

‡ A full physical/clinical examination will be conducted on each vaccination visit (before vaccine injection), and at the Investigator's discretion at the time of other visits, based on the health status of the subject.

§ Subject's temperature is to be measured before each injection, and at the Investigator's discretion at the time of other visits, based on the health status of the subject. Temperatures will be recorded in source document only.

** Concomitant therapy will be collected for Days 7, 14 and 28 days post-Injection 1 as well as before and 28 days after Injection 2 and Injection 3.

†† In all female subjects, result of urine pregnancy test should be confirmed as negative before each vaccine injection.

‡‡ Screening tests will be performed at local laboratory within 4 weeks before the first vaccination. These tests will include: serology (HBsAg, HCV Ab), hematology (hemoglobin, hematocrit, platelet count, white blood cells count), and biochemistry (AST, ALT, urea and creatinine). HBsAg and HCV tests will not be performed in case the information is already available in subject's medical history. If serology, hematology, and biochemistry results are available and were obtained within 4 weeks before first injection, tests do not need to be performed again.

§§ Tests will be performed sequentially. RDT will be performed first, and IgG ELISA will only be performed on subjects who tested negative for RDT. Subjects who previously tested negative by RDT can be re-screened using dengue IgG ELISA.

*** Blood sample to be collected before vaccine injection.

††† Pre-injection CD4 count and HIV viral load will come from routine periodical tests of subjects as per local guidelines. For subjects for whom HIV viral load and CD4 count have not been assessed within 2 months before the Screening Visit, the Investigator will perform tests to ensure that results are available at the time of Visit 1. Likewise, if HIV viral load and CD4 count have not been tested within 2 months before Inj 2 or Inj 3 (for checking contraindication) the Investigator will perform tests to ensure that results are available before the corresponding vaccination visit.

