5.1 Description of the Overall Study Design and Plan

5.1.1 Study Design

This is a multi-center, observer-blind, randomized, placebo-controlled, Phase II study of the CYD dengue vaccine in 150 HIV-positive adults (18 to 50 years) in Brazil. Potential participants fulfilling all inclusion criteria, including a previous exposure to dengue according to the RDT or ELISA, will be enrolled. Subjects will receive 3 injections of either CYD dengue vaccine or placebo at 0, 6, and 12 months. The enrollment of subjects will be carried out in 2 steps, including an early safety data review (ESDR) before the second step.

Subjects HIV-positive and previously exposed to dengue according to RDT or ELISA will be randomized in a 2:1 ratio into 1 of 2 groups:

- Group 1 (N=100): subjects will receive 3 doses of CYD dengue vaccine (live, attenuated, dengue serotype 1, 2, 3, 4 virus)
- Group 2 (N=50): subjects will receive 3 doses of placebo (NaCl 0.9%)

Each subject will have her / his dengue serostatus confirmed using dengue PRNT and anti-NS1 IgG assay on the pre-injection blood sample. Subjects who are dengue-positive by RDT or ELISA at Screening Visit and dengue-negative by PRNT (sample collected before the first injection [at Visit 1] and assayed before second injection) will be considered as not previously exposed. Therefore, they will not receive any further injections and will be followed for safety until 6 months after the last dose. In addition, if they received the vaccine, provisions for timely access to medical care will be offered for 10 years after the last dose, according to IDMC prior recommendations.

All subjects are planned to be included in safety and immunogenicity analysis set. Blood samples will be taken at the Screening Visit (serology, hematology, biochemistry), and at several other time points throughout the study for baseline dengue, YF, and Zika serological status, CYD

dengue vaccine immunogenicity, dengue vaccinal viremia post-Inj 1, and HIV status monitoring assessments, depending on the time points. More details are provided in [Section 5.1.3](#).

The duration of each subject's participation in the study will be approximately 18 months.

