5.2.7 Contraindications for Subsequent Vaccinations

The CYD dengue vaccine should not be administered to seronegative persons.

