7.1.1.1 Blood Sample for Screening Characteristics Assessment

Approximately 14 mL (according to local laboratories) of blood will be collected from potential subjects in order to perform laboratory tests, including assessment of previous exposure to dengue, HBsAg, HCV Ab, hematology (hemoglobin, hematocrit, platelet count, white blood cells

count), biochemistry (AST, ALT, urea, and creatinine)^a. For subjects for whom HIV viral load and CD4 count have not been assessed within 2 months before the Screening Visit, an additional volume of blood (10 mL per test) will be required before the Screening Visit to perform the tests. The screening analyses will be performed at local laboratories. For subjects for whom these tests have been performed in appropriate time windows (within 4 weeks before injection for hepatitis serology, hematology, and biochemistry; within 2 months for HIV viral load and CD4 count) as part of the subject's routine follow-up, no new tests will be required.

Also, subject' previous exposure to dengue will be assessed using a RDT (OnSite™ Dengue IgG/IgM3.0 Combo Rapid Test commercialized by CTK Biotech, Inc.) or ELISA (Anti-Dengue IgG ELISA commercialized by Euroimmun).

7.1.1.2 Blood Sample for Dengue, YF, and Zika Serostatus, Dengue Neutralizing Antibodies, CD4 Count, and HIV Viral Load Assessments

At V01 (before first vaccination injection) for all subjects, 9 mL of blood will be collected in order to assess dengue, YF, and Zika status, as well as baseline dengue neutralizing Ab levels (PRNT).

At V04, V06, and V08 for all subjects, 24 mL of blood will be collected in order to assess dengue neutralizing Ab levels, CD4 count, and HIV viral load, 28 days post-injection. See [Table 5.1](#) for blood samples volumes for each laboratory test.

In addition, for subjects for whom HIV viral load and CD4 count have not been assessed within 2 months before Inj 2 (Visit 5) or Inj 3 (Visit 7), an additional volume of blood (10 mL per test) will be required before injection visits to perform the tests and check the contraindication to further vaccination. The tests will be performed at local laboratories.

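### Visit 1 does not make randomisation and injection depend on obtaining the pre-injection blood sample, and no rule covers a missing baseline PRNT at dose 2

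*Protocol*

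**What the plan says.** Protocol Section 5.1.4 treats a failed blood draw differently at the two visits before the first injection.

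- **Screening, step 7.** After further attempts within the window, the reason goes into the source document, and then "In that case, the subject will not participate in the study".
- **Visit 1, step 8.** After another attempt, "If a blood sample cannot be obtained, the reason will be recorded in the blood sampling page of the CRF". Step 9 is the IRT contact for the assigned product and step 10 is "Inject the appropriate investigational product". Neither refers back to step 8.

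Other places state the intended timing and coverage of the Visit 1 sample. A footnote to the Table of Study Procedures reads "Blood sample to be collected before vaccine injection", and Section 7.1.1.2 reads "At V01 (before first vaccination injection) for all subjects, 9 mL of blood will be collected". Neither says what follows if the sample cannot be obtained.

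The sample has a later use. Section 5.1.1 (repeated in SAP Section 3.1) stops further injections for a subject who is PRNT-negative on the "sample collected before the first injection [at Visit 1] and assayed before second injection". Visit 5, step 5, tells the site: "Check for confirmation of previous exposure to dengue (from PRNT laboratory results". Section 5.2.7 opens with "The CYD dengue vaccine should not be administered to seronegative persons".

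**The concern.** BL1 is the only sample on which the plan schedules a baseline dengue PRNT, anti-NS1 IgG, and YF and Zika neutralizing antibodies. A subject injected without it reaches Visit 5 with nothing to check. Section 5.1.1 attaches a consequence to a negative PRNT but none to an absent one. An absent result also appears in neither the temporary nor the definitive contraindications (Sections 5.2.7.1 and 5.2.7.2). Sites could then act differently.

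The same PRNT result identifies the vaccinees to whom Section 5.1.1 offers ten years of access to medical care. A truly unexposed vaccinee without BL1 could not be found by PRNT, and so could miss both the stop on further injections and that provision. Sections 1.2 and 1.3.2 describe a raised risk of hospitalized and severe dengue in unexposed vaccinees.

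On the analysis side, the subject has no baseline titer and hence no ratio to baseline.

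**Working it through.** This is mainly a reading of procedures. The only design probability in the documents is the 95% chance of seeing an event of 3% incidence among 100 vaccinees. It reproduces (1 − 0.97^100 = 0.952), and this point does not affect it.

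**1. Is there a stop at Visit 1?** Screening states one and Visit 1 does not. The only postponement at Visit 1 is a single one for temporary ineligibility, and a failed draw is not described as ineligibility. Inclusion criterion 3 (ability to comply with study procedures) is general and is not tied to this draw.

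**2. Could another planned sample stand in?**
- Samples taken to qualify a subject for inclusion are for immediate use (Section 7.4), and no PRNT on them is planned.
- Section 1.2 describes inferring baseline serostatus by anti-NS1 IgG on serum from about one month after the third dose. In this trial anti-NS1 is an endpoint at baseline only (Section 9.3.1.1). Used as described there, it would come after the dose-2 decision, and it gives no PRNT titer.

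**3. Would Screening already exclude people who are hard to bleed?** Only in part. By Table 5.1 the full screening draw is 5 + 3 + 5 + 1 = 14 mL. Where routine results are in date, only the 1 mL dengue sample may be needed, against 5 + 2 + 2 = 9 mL at Visit 1.

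**4. What is lost in analysis?**
- Titer ratios per subject: Protocol Section 12.1.2.2 lists two time points, so 4 serotypes × 2 = 8. SAP Section 5.1.2.2 lists three, so 4 × 3 = 12. All use the pre-Injection 1 titer as denominator.
- Missing values are not imputed (Protocol 12.3.2, SAP 5.3.2).
- The serology criteria of the FAS and PPAS name post-injection samples only. The subject can therefore count in post-dose GMTs while absent from the baseline GMT and the ratios.
- With no BL1 result, SAP Section 4.4.2.3 places the subject in the missing category for baseline status.
- Safety data are unaffected.

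**5. How many subjects?** The documents give no failed-draw rate, so the rate *m* is an assumption. The expected number is 150*m* overall and 100*m* on vaccine. The chance of at least one among 150 is 1 − (1 − *m*)^150.

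| Assumed *m* | Expected of 150 | Expected of 100 on vaccine | Chance of at least one of 150 |
|---|---|---|---|
| 0.5% | 0.75 | 0.5 | 53% |
| 1% | 1.5 | 1.0 | 78% |
| 2% | 3.0 | 2.0 | 95% |

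**6. How many of these would be unexposed vaccinees?** All have a positive RDT or ELISA. If, as a further assumption, 5% to 10% of screen-positives were false positives, the expected number runs from 0.5 × 0.05 = 0.025 to 2 × 0.10 = 0.2 subjects.

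**The case against.** The strongest reply is that the sample is required elsewhere. It is to be drawn before injection, for all subjects, and Section 5.1.1 says every subject's serostatus will be confirmed on it. The draw precedes the injection in the step order. Detailed randomisation procedures are in the Operating Guidelines (Section 6.5), which are not available here, so an IRT check cannot be ruled out. The Visit 5 step looks for confirmation, and an absent result does not confirm anything. This stands as evidence of intent, and a careful site might well defer. It does not supply the missing rule: nothing in the protocol or SAP makes the injection wait, or says what an absent result means at Visit 5.

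Four stronger readings are tempting, and the documents do not support them.

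- *The protocol instructs sites to inject without the sample.* It is silent; it does not direct this.
- *The wording was carried over unchanged from the post-injection visits.* Only the closing sentence matches. Those visits limit the further attempt to the visit window and Visit 1 does not, which leaves some room to defer.
- *Serostatus can never be recovered.* This holds for the baseline PRNT titer. It is too broad for serostatus, given the anti-NS1 approach in Section 1.2, although that is not planned here as a fallback.
- *Every affected vaccinee is a seronegative person put at risk.* All are RDT- or ELISA-positive, and both tests were chosen for high specificity. Dose 1 is given before the PRNT result is known for everyone by design, so the gap concerns later doses only.

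It is also fair to say that the analysis loss is ordinary missing data in a descriptive study with no hypothesis tests.

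**Conclusion.** The point holds as a narrow procedural gap that is worth closing. As written, Visit 1 lets a subject be randomised and injected without the one sample planned for the dose-2 PRNT check, the titer-ratio denominator and baseline flavivirus status, and no passage gives an outcome for a missing baseline PRNT.

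The size is probably small: 0.75 to 3 of 150 subjects if 0.5% to 2% of Visit 1 draws fail, with truly unexposed vaccinees among them fewer still. Both the failure rate and the false-positive share are assumptions. The sample-size statement and the primary safety analysis are unaffected. The case for change rests on the loss of the protocol's own confirmation step for each such subject, and on how little the change costs.

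**What to change.** In Protocol Section 5.1.4, Visit 1:

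1. Make the IRT randomisation call (step 9) follow a confirmed BL1 draw, with a matching IRT prompt.
2. Extend the single-postponement wording, now limited to temporary ineligibility, to a failed draw.
3. Align the outcome of a persistent failure with the rule already stated for Screening.

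A successful draw can still give no reportable result. The sponsor should therefore also reconcile the Table of Study Procedures footnote, Section 5.1.1, Visits 1 and 5 in Section 5.1.4, and Sections 5.2.7 to 5.2.7.2 for a subject whose baseline PRNT is missing or not reportable at Visit 5. Which clinical rule should apply is for the sponsor to decide and is not proposed here.

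The cost is a few sentences and one IRT prompt. The downside is that a very few people are deferred or not randomised.
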